## **11. DESCRIPTION OF GLOBAL AMENDMENT(S)**

### **11.1 GLOBAL AMENDMENT 1**

Number of global amendment	1
Date of CTP revision	10 February 2017
EudraCT number	2015-004412-38
BI Trial number	1160.248
BI Investigational Product(s)	Pradaxa®, dabigatran etexilate
Title of protocol	RE-SPECT CVT: a randomised, open-label, exploratory trial with blinded endpoint adjudication (PROBE), comparing efficacy and safety of oral dabigatran etexilate versus oral warfarin in patients with cerebral venous and dural sinus thrombosis over a 24-week period
To be implemented only after approval of the IRB / IEC / Competent Authorities	X
To be implemented immediately in order to eliminate hazard – IRB / IEC / Competent Authority to be notified of change with request for approval	
Can be implemented without IRB / IEC / Competent Authority approval as changes involve logistical or administrative aspects only	
Section to be changed	Clinical Trial Protocol Synopsis 3.3 SELECTION OF TRIAL POPULATION 7.7 DETERMINATION OF SAMPLE SIZE
Description of change	No. of patients was changed from total 180 planned to total 120 planned and from 90 to 60 planned in each treatment arm The anticipated drop-out rate was changed from 15-20% to 10%, resulting in 108 evaluable patients (54 per treatment arm)
Rationale for change	Due to the exploratory nature of the trial the total number of required patients is difficult to determine. During trial preparation it became clear that the trial may be conducted with fewer patients than originally assumed. Since it would be

Proprietary confidential information © 2017 Boehringer Ingelheim International GmbH or one or more of its affiliated companies

		considered unethical to put more patients at risk than is required, the number was reduced. The drop-out rate was updated based on experience of the trial's Steering Committee members
Section to be changed		Flow Chart, footnote 8 5.3.3 Safety laboratory parameters
Description of change		Text about pregnancy testing was changed to clarify that all WOCBP should perform a pregnancy test every 4 weeks (instead of only women randomised to warfarin)
Rationale for change		Request from authorities and simplification of instructions for trial sites
Section to be changed		3.3.2 Inclusion criteria 4.2.2.4 Restrictions regarding women of childbearing potential
Description of change		Addition of a list of acceptable contraception methods to section 4.2.2.4 and Inclusion criterion 2 was updated to include a reference to that list; Removal of tubal ligation from the list of procedures to render a woman not of childbearing potential; Addition of text (section 4.2.2.4) to specify that WOCBP should use effective methods of birth control from the moment of signing informed consent for the trial until completion of the follow-up visit (Visit 6)
Rationale for change		Request from the authorities and adaptation to recently updated recommendations from the European Union Heads of Medicines Agency related to contraception and pregnancy testing in clinical trials (CTFG, 2014)
Section to be changed		2.2 TRIAL OBJECTIVES
Description of change		Clarification that the primary objective does not require 24 weeks of treatment
Rationale for change		To be consistent with the description of the trial's endpoints: the primary endpoint will be assessed up to 24 weeks after randomisation irrespective of whether or not treatment was taken for 24 weeks.
Section to be changed		3.1.1 Administrative structure of the trial 3.2 DISCUSSION OF TRIAL DESIGN, INCLUDING THE CHOICE OF CONTROL GROUP(S)
Description of change		Change in set-up of the adjudication committee
Rationale for change		For this exploratory trial the adjudication committee (AC) for central assessment of endpoints will be set-up by the sponsor, hiring

Proprietary confidential information © 2017 Boehringer Ingelheim International GmbH or one or more of its affiliated companies

	external experts. By not using a third party vendor for AC coordination, the AC may not be considered completely independent of the sponsor by all stakeholders, although all decisions made by AC members will not be influenced by the sponsor. Therefore the description of the AC is changed.
Section to be changed	4.1.4 Drug assignment and administration of doses for each patient
Description of change	Addition of caution statement about treatment with warfarin in patients with known protein C or protein S deficiency
Rationale for change	Request from authorities
Section to be changed	5.2.1 Venous thrombotic events
Description of change	The requirements for confirmation of DVT, PE and splanchnic vein thrombosis were changed to require images and/or reports (instead of both) to be provided to the AC
Rationale for change	In order to be in line with what was done in prior trials with the same IMP, and in order to limit the source data transfer to the necessary elements required for adjudication
Section to be changed	7.3 PLANNED ANALYSES
Description of change	An additional patient population, Screened Set (SCR), was defined, i.e. All patients who sign informed consent and complete at least some screening procedures.
Rationale for change	This patients set will be used for display of disposition tables etc.
Section to be changed	8.3.1 Source documents
Description of change	Deletion of the list of documents and images that will be made available for adjudication purposes
Rationale for change	This will be defined in the adjudication charter instead of the trial protocol

2. LIST OF ABBREVIATIONS

Term	Definition / description
AC	Adjudication committee
ADS	Analysis Datasets
AE	Adverse event
BRPM	Blinded report planning meeting
CI	Confidence interval
CrCl	Creatinine clearance
CRNMBE	Clinically relevant non-major bleeding event
CTP	Clinical trial protocol
CTR	Clinical trial report
CVT	Cerebral venous or dural sinus thrombosis
DBL	Database lock
DMC	Data Monitoring Committee
DVT	Deep vein thrombosis
ECG	Electrocardiogram
eCRF	Electronic case report form
EMA	European Medicines Agency
EOT	End of treatment
FAS	Full analysis set
HI	Haemorrhagic infarction
HR	Hazard ratio
ICH	International Conference on Harmonisation
"ICH"	Intracranial haemorrhage
INR	International normalised ratio
IPV	Important protocol violation
IRT	Interactive response technology
ISTH	International Society on Thrombosis and Haemostasis
ITT	Intent-to-treat
LMWH	Low molecular weight heparin
MBE	Major bleeding event
MedDRA	Medical Dictionary for Regulatory Activities

 TSAP for BI Trial No: 1160.248
 Page 5 of 30

 Proprietary confidential information © 2018 Boehringer Ingelheim International GmbH or one or more of its affiliated companies

Term	Definition / description
MRI	Magnet resonance imaging
NIHSS	National Institutes of Health Stroke Scale
PE	Pulmonary embolism
PH	Parenchymatous haematoma
PN	Preferred name
PPS	Per protocol set
PROBE	Prospective, randomised, open label, blinded endpoint
PSTAT	Project statistician
РТ	Preferred term
PV	Protocol violation
Q1	Lower quartile
Q3	Upper quartile
REP	Residual effect period
SA	Statistical analysis
SCR	Screened set
SD	Standard deviation
SMQ	Standardised MedDRA query
SOC	System organ class
TCM	Trial clinical monitor
TSAP	Trial statistical analysis plan
TTR	Time in therapeutic range
UFH	Unfractionated heparin
VKA	Vitamin K antagonist(s)
VTE	Venous thrombotic event
WHO-DD	World Health Organisation – Drug Dictionary

3. INTRODUCTION

As per ICH E9 [2], the purpose of this document is to provide a more technical and detailed elaboration of the principal features of the analysis described in the protocol, and to include detailed procedures for executing the statistical analysis (SA) of the primary and secondary variables and other data.

This trial statistical analysis plan (TSAP) assumes familiarity with the clinical trial protocol (CTP) [11], including protocol amendments. In particular, the TSAP is based on the planned analysis specification as written in CTP Section 7 "Statistical Methods and Determination of Sample Size". Therefore, TSAP readers may consult the CTP for more background information on the study, e.g., on study objectives, study design and population, treatments, definition of measurements and variables, planning of sample size, randomization.

This TSAP does not cover the planned data review by the Data Monitoring Committee (DMC). A separate DMC SAP was produced for this purpose.

SAS[®] Version 9.4 will be used for all analyses.

4. CHANGES IN THE PLANNED ANALYSIS OF THE STUDY

In the CTP version 1 only three analysis populations have been defined: treated set (TS), full analysis set (FAS) and per protocol set (PPS). A screened set (SCR) as described in CTP version 2 (01FEB2017) will also be created for display of disposition tables, etc., see Section 6.3.

5. ENDPOINT(S)

5.1 **PRIMARY ENDPOINT(S)**

The primary endpoint for this trial is the number of patients with the composite of major bleeding event (MBE) according to International Society on Thrombosis and Haemostasis (ISTH) criteria or venous thrombotic event (VTE: recurring cerebral venous or dural sinus thrombosis (CVT), deep vein thrombosis (DVT) of any limb, pulmonary embolism (PE), splanchnic vein thrombosis) up to 24 weeks.

All components of the primary endpoint will be adjudicated by an independent adjudication committee (AC). Details of the adjudication criteria can be found in the adjudication charter. All endpoints are either explicitly collected in the electronic case report form (eCRF) or captured in the database following adjudication. Adjudicated data takes precedence over eCRF data where both are available.

ISTH definition of an MBE:

• Symptomatic bleeding in a critical area or organ, such as intracranial, intraspinal, intraocular, retroperitoneal, intra-articular or pericardial, or intramuscular with compartment syndrome or other critical location

and/or

• Bleeding associated with a reduction in haemoglobin of at least 2g/dL (1.24mmol/L) within 24 hours, or leading to transfusion of two or more units of blood or packed cells

and/or

• Fatal bleed

5.2 SECONDARY ENDPOINT(S)

5.2.1 Key secondary endpoint(s)

Not defined.

5.2.2 (Other) Secondary endpoint(s)

All secondary endpoints will be based on adjudicated data (except for any bleeding event).

The secondary efficacy endpoints are:

- Number of patients with recurring VTE (CVT, DVT of any limb, PE or splanchnic vein thrombosis) up to 24 weeks
- Cerebral venous recanalisation as measured by the change in number of occluded cerebral veins and sinuses up to 24 weeks

The secondary safety endpoints are:

- Number of patients with MBE according to ISTH criteria up to 24 weeks
- Composite endpoint of number of patients with new intracranial haemorrhage (also abbreviated as "ICH") or worsening of the haemorrhagic component of a previous lesion up to 24 weeks (categorisation see Table 5.2.2: 1)

- Number of patients with clinically relevant non-major bleeding event (CRNMBE) up to 24 weeks
- Number of patients with MBE according to ISTH criteria or CRNMBE up to 24 weeks
- Number of patients with any bleeding event up to 24 weeks

Recanalisation will be assessed as described below, analogous to the calculations made by Miranda et al [12].

- 1. At baseline and at the end of treatment EOT, occlusion of cerebral veins and sinuses will be scored as follows:
 - 1 =full occlusion
 - 0 = no occlusion or partial occlusion
- 2. This score will be applied to each of the veins and sinuses using the below conventions:
 - Superior sagittal sinus, straight sinus, cavernous sinus, left jugular vein, right jugular vein will each be scored individually (i.e. each will be scored as either 0 or 1)
 - Right lateral transverse and sigmoid sinus will be scored together (i.e. 0 points if neither is fully occluded; 1 point if at least one of them is fully occluded)
 - Left lateral transverse and sigmoid sinus will be scored together (i.e. 0 points if neither is fully occluded; 1 point if at least one of them is fully occluded)
 - Superior petrous sinus and inferior petrous sinus will be scored together (i.e. 0 points if neither is fully occluded; 1 point if at least one of them is fully occluded)
 - Deep venous system will be scored as system, irrespective of the number of occluded veins (i.e. 0 points if none is fully occluded; 1 point if at least one is fully occluded)
 - Superficial cortical veins will be scored as system, irrespective of the number of occluded veins (i.e. 0 points if none is fully occluded; 1 point if at least one is fully occluded)
 - Cerebellar veins will be scored as system, irrespective of the number of occluded veins (i.e. 0 points if none is fully occluded; 1 point if at least one is fully occluded)
- 3. For each individual patient a total score will be calculated at baseline and at the EOT.
- 4. A recanalisation score will subsequently be calculated for each patient as the difference between the baseline total score and the EOT total score.

Page 10 of 30

Proprietary confidential information © 2018 Boehringer Ingelheim International GmbH or one or more of its affiliated companies

Table 5.2.2: 1	Categorisation o	f haemorrhagic br	rain lesions (Vo	on Kummer et al [13])
----------------	------------------	-------------------	------------------	-----------------------

Class	Туре	Description
1	Haemorr	hagic transformation of infarcted brain tissue
1a	HI-1*	Scattered small petechiae, no mass effect
1b	HI-2	Confluent petechiae, no mass effect
1c	PH-1*	Haematoma within infarcted tissue, occupying <30%, no substantive mass effect
2	Intracerebral haemorrhage within and beyond infarcted brain tissue	
	PH-2	Haematoma occupying 30% or more of the infarcted tissue, with obvious mass effect
3	Intracerebral haemorrhage outside the infarcted brain tissue or intracranial-extracerebral haemorrhage	
3a	Parenchymal haematoma remote from infarcted brain tissue	
3b	Intraventricular haemorrhage	
3c	Subarachnoid haemorrhage	
3d	Subdural haemorrhage	

* HI: haemorrhagic infarction; PH: parenchymatous haematoma

Any new haemorrhagic brain lesion will be categorised as Class 3 (Intracerebral haemorrhage outside the infarcted brain tissue or intracranial-extracerebral haemorrhage). If there is more than one haemorrhagic lesion present on imaging, the category of the most severe lesion is assigned.

For each patient, intracranial haemorrhage will be classified at baseline and EOT (in case there is no EOT visit, the classification based on the last on-treatment images up to 6 days after last study drug intake will be taken for the determination of worsening).

Worsening is defined as follows:

- Class 3 is worse than class 2, which is worse than class 1.
- Within class 1, type PH-1 (1c) is worse than type HI-2 (1b), which is worse than type HI-1 (1a).
- Within class 3 (a, b, c, d), an increase of at least 25% in volume is considered a worsening.

Patients who died during the trial before an EOT scan is made and patients for whom for other reasons no EOT or on-treatment scan is available or analysable will not be included in the analysis of number of patients with new intracranial haemorrhage or worsening of the haemorrhagic component of a previous lesion.

TSAP for BI Trial No: 1160.248 Page 11 of 30 Proprietary confidential information © 2018 Boehringer Ingelheim International GmbH or one or more of its affiliated companies

ISTH definition of a CRNMBE:

A CRNMBE is a clinically overt bleed that does not meet the criteria for an MBE but prompts a clinical response, in that it leads to at least one of the following:

A hospital admission (i.e overnight stay in the hospital) for bleeding •

or

A physician guided medical or surgical treatment for bleeding •

or

A physician guided change, interruption or discontinuation of trial medication •

 TSAP for BI Trial No: 1160.248
 Page 12 of 30

 Proprietary confidential information © 2018 Boehringer Ingelheim International GmbH or one or more of its affiliated companies

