### **3.3.4 Removal of patients from therapy or assessments**

#### **3.3.4.1 Removal of individual patients**

It is important to distinguish between premature study drug discontinuation and premature study discontinuation.

Patients can stop study drug for various reasons as described below however they should be encouraged to re-start study medication at the Investigator's discretion and when he/she considers it safe to do so.

Regardless of whether or not study drug continues to be taken, patients will continue to participate in regularly scheduled follow-up visits and assessments until 25 weeks after randomisation, unless they withdraw their consent to do so. Patients not actively taking study drug are strongly encouraged to continue trial participation,

and report events that comprise the primary endpoint at minimum.

Data collected for all randomised patients will be used in the analysis. This includes randomised patients who never take study medications and patients that prematurely discontinue study drug. Procedures to be followed for patients prematurely terminating the trial are detailed in Section [6.2.3](#). Patients that withdraw from trial participation or study drug will not be replaced.

If study drug is permanently stopped, patients should attend two follow-up visits. Refer to Section 6.2.3 for further details.

An individual patient is to be withdrawn from trial treatment if:

---

 Patients having received recent hepatitis B vaccination and thus testing positive for these antibodies will not be excluded.

Proprietary confidential information © 2017 Boehringer Ingelheim International GmbH or one or more of its affiliated companies

- The patient withdraws consent for trial treatment or trial participation, without the need to justify the decision.
- The patient becomes pregnant.
- The patient needs to take concomitant drugs that interfere with the investigational product or other trial medication (see Section [4.2.2](#)).
- Patients randomised to receive dabigatran who are found to have a CrCl <30mL/min during the course of the trial should have trial medication temporarily discontinued (see Section [5.3.3](#) for calculation of CrCl). Labs can be repeated before stopping trial medication if Investigator wishes to confirm initial lab result. The patient will be permanently discontinued from trial medication, unless CrCl recovers to  $\geq 30$ mL/min within seven days.  

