Patients who died during the trial before an EOT scan is made and patients for whom for other reasons no EOT scan is available or analyzable will not be included in the analysis of recanalisation (this applies to change in number of occluded cerebral veins and sinuses)

Diagnosis of CVT and assessment of venous occlusion is expected to be performed by any of the following techniques or a combination of them:

- MRI + MR venography
- CT + CT venography
- MRI or CT in combination with angiography (DSA)

Patients are diagnosed prior to trial entry. The imaging that was performed for diagnosis of CVT (as part of the clinical routine) will be used as baseline assessment.

At EOT the assessment of recanalisation must be done by MRI+MR venography. These techniques are expected to provide a better view of any remaining venous occlusion than CT would. Furthermore, for WOCBP it is desirable to refrain from CT scans in the non-acute setting due to radiation exposure of CT scans.

A separate MRI protocol will be provided as part of the ISF and should be followed for the EOT imaging.

All scans (both baseline and EOT) will be sent in for central review by the AC. Review criteria will be outlined in the AC charter governing the adjudication process. Details on how to provide the images will be provided in the ISF. Central review will focus on assessment of endpoints (grade of cerebral venous recanalisation / recurrence of CVT).

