### **5.3.5      Other safety parameters (safety endpoints)**

#### **5.3.5.1      Composite endpoint of new haemorrhagic brain lesion or worsening of the haemorrhagic component of a previous lesion**

The neuroimaging which established the diagnosis of CVT will be used as baseline value. The safety endpoint "new haemorrhagic brain lesion or worsening of the haemorrhagic component of a previous lesion" will be assessed by comparing repeated neuroimaging that is routinely performed if the patient has a neurological worsening during the trial, or at the EOT visit, to the baseline image. The comparing of images and the categorisation of the lesions (see below) will be done by the AC.

A separate MRI protocol will be provided as part of the ISF and should be followed for the EOT imaging.

In order to assess any worsening of previous lesions, haemorrhagic brain lesions at baseline and during treatment / at EOT will be categorised as indicated in Table [5.3.5.1: 1](#) below, according the definitions as recommended by Von Kummer et al [[P15-09432](#)]:

Table 5.3.5.1: 1      Categorisation of haemorrhagic brain lesions

Class	Type	Description
1		Haemorrhagic transformation of infarcted brain tissue
1a	HI-1*	Scattered small petechiae, no mass effect
1b	HI-2	Confluent petechiae, no mass effect
1c	PH-1*	Haematoma within infarcted tissue, occupying <30%, no substantive mass effect
2		Intracerebral haemorrhage within and beyond infarcted brain tissue
	PH-2	Haematoma occupying 30% or more of the infarcted tissue, with obvious mass effect
3		Intracerebral haemorrhage outside the infarcted brain tissue or intracranial-extracerebral haemorrhage
3a		Parenchymal haematoma remote from infarcted brain tissue
3b		Intraventricular haemorrhage
3c		Subarachnoid haemorrhage
3d		Subdural haemorrhage

\* HI: haemorrhagic infarction; PH: parenchymatous haematoma

Any new haemorrhagic brain lesion will be categorised as Class 3 (Intracerebral haemorrhage outside the infarcted brain tissue or intracranial-extracerebral haemorrhage).

If there is more than one haemorrhagic lesion present on imaging, the category of the most severe lesion is assigned.

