### 7.3.2 Secondary endpoint analyses

Secondary analyses will be based on the FAS for the following endpoints: number of patients with CVT, DVT, PE, splanchnic vein thrombosis and the endpoint on cerebral venous recanalisation as measured by the change in number of occluded cerebral veins and sinuses after up to 24 weeks.

The following analyses will be based on the treated set: number of patients with major bleeding according to ISTH, number of patients with clinically relevant non-major bleeding, as well as the composite of the two mentioned above, number of patients with any bleeding, number of patients with composite endpoint of new ICH or worsening of the haemorrhagic component of a previous lesion.

The analyses for the secondary endpoints as described in Section [5.1.2](#) will be mainly based on frequency counts and percentages along with 95% confidence intervals.

Means and standard deviations will be displayed by treatment arm for the endpoint on cerebral venous recanalisation as measured by the change in number of occluded cerebral

veins and sinuses after up to 24 weeks. Means and standard deviations will be displayed by stratification factor of presence or absence of ICH at baseline. Patients with missing or not analysable MRI scans at EOT would need to be excluded from this analysis.

The composite endpoint of new ICH or worsening of the haemorrhagic component of a previous lesion will be categorized as described in Section [5.3.5.1](#). This ordinal endpoint will be analysed with Cochrane-Mantel-Haenszel test.

Further specification of analyses can be found in the TSAP.

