6.3 PATIENT SETS ANALYSED

The following analysis sets will be defined for this trial:

- Screened set (SCR) All patients who signed informed consent; these patients will have completed routine procedures to establish the diagnosis of CVT.
- Treated set (TS): The set includes patients who received at least one dose of study medication.
- Full analysis set (FAS): This set includes all patients randomised.
- Per protocol set (PPS): This is a subset of the TS, restricted to patients without relevant important protocol violations as defined in Table 6.2: 1.

Proprietary confidential information © 2018 Boehringer Ingelheim International GmbH or one or more of its affiliated companies

The efficacy analysis (i.e. analysis of primary and secondary efficacy endpoints, as well as further endpoints based on the FAS will follow the intent-to-treat (ITT) principle. Patients will be allocated to the randomised treatment groups regardless of actual medication taken.

The safety analysis (including analysis of secondary safety endpoints

as well as adverse event analysis) will be based on the TS, and patients will be analyzed according to the treatment they have received.

Secondary efficacy analysis on the PPS may not be conducted if the number of patients excluded from the patient set is small (i.e. <10% of the TS).

Disposition data on the SCR will be presented according to the randomized treatment groups. For patients not entered/randomised on the total number will be presented.

			· · , ,	
		Pa	itient set	
Class of endpoint/data	SCR	TS	FAS	PPS
Primary endpoint (Section 5.1)			primary analysis	secondary analysis
Secondary and further efficacy endpoints (Section 5.2.2 and 5.3)			X	
Safety endpoints (Section 7.8)		Х		
Demographic/baseline data (Section 7.1)		Х	(X)	
Disposition	Х			

Table 6.3: 1Patient sets analyzed

(X) An additional FAS presentation of the demographic/baseline data may be provided in the End of Text section of the clinical trial report (CTR) if patient numbers for FAS and TS are clearly different, i.e. if $\geq 10\%$ of the TS are excluded from the FAS.

Note that the number of patients with available data for an endpoint may differ. For details, see Section 6.6 "Handling of missing data and outliers".

Proprietary confidential information © 2018 Boehringer Ingelheim International GmbH or one or more of its affiliated companies

Page 19 of 30

6.5 **POOLING OF CENTRES**

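### SAP 5.2.2 as worded drops patients who died before an end-of-treatment scan from the new or worsening intracranial haemorrhage analysis, even when an on-treatment scan could classify them

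*SAP*

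**What the plan says.** SAP 5.2.2 classifies each patient's haemorrhage at baseline and at EOT, with a fallback: "in case there is no EOT visit, the classification based on the last on-treatment images up to 6 days after last study drug intake" is used to judge worsening. The fallback makes no exception for death.

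The next paragraph of SAP 5.2.2 removes two groups from the analysis of new or worsening ICH: "Patients who died during the trial before an EOT scan is made and patients for whom for other reasons no EOT or on-treatment scan" exists in usable form.

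Protocol 5.3.5.1 takes the imaging for this endpoint from "repeated neuroimaging that is routinely performed if the patient has a neurological worsening during the trial, or at the EOT visit", compared with the diagnostic scan. Flow Chart footnote 11 sends images taken for clinical worsening or suspected new ICH to the Adjudication Committee throughout the trial.

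Protocol 5.2.6 contains nearly the same exclusion sentence: "Patients who died during the trial before an EOT scan is made and patients for whom for other reasons no EOT scan is available", with unreadable scans treated likewise. There its scope is stated: these patients "will not be included in the analysis of recanalisation (this applies to change in number of occluded cerebral veins and sinuses").

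The protocol gives no missing-scan rule for the haemorrhage endpoint. Protocol 7.3.2 says "Further specification of analyses can be found in the TSAP".

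**The concern.** The exclusion sentence has two limbs. The first is triggered by death before an EOT scan and sets no condition on other scans. The second is triggered by having no usable scan, and only there does an on-treatment scan count. A patient imaged at neurological worsening, adjudicated as having new or worse haemorrhage, who then dies before any EOT scan, falls under the first limb and leaves the analysis.

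Exclusion would then depend on an outcome that the measured event can itself cause, in a safety endpoint of an anticoagulant trial. It would also leave whoever derives the endpoint with two instructions in one section that give different answers for the same patient. In the worst case, the ICH table for an arm could show no event while the major-bleeding table for that arm shows a fatal intracranial one.

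**Working it through.** The plan states no figure for this rule, so there is none to reproduce. The check is a comparison of the sentences, followed by an illustration of size.

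**Step 1. Apply both SAP 5.2.2 sentences to each type of patient.**

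| Patient | Fallback sentence | Exclusion sentence, as worded |
|---|---|---|
| Has an analysable EOT scan | Not needed; classified at EOT | Kept |
| Survived, no EOT visit, analysable on-treatment scan | Classified from that scan | Kept |
| Died before an EOT scan, analysable on-treatment scan | Classified from that scan | Excluded |
| No analysable EOT or on-treatment scan, alive or dead | Cannot be classified | Excluded |

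Only the third row conflicts. Rows two and three can have identical images and differ only in survival.

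**Step 2. Is death a case the fallback should cover?** Flow Chart footnote 3 has EOT procedures done for all patients when trial medication stops, including those who stop early. A survivor who stops should therefore have an EOT visit. Death on treatment is a plain way to have none.

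**Step 3. Compare with Protocol 5.2.6.** The SAP sentence matches the protocol's recanalisation sentence, with the on-treatment scan added to the second limb only and a different endpoint named. For recanalisation the death limb is coherent, because the score is the baseline total minus the EOT total and cannot exist without an EOT scan. For haemorrhage, Protocol 5.3.5.1 also accepts a worsening scan, so death before EOT does not by itself make the endpoint unassessable.

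**Step 4. Size, on assumed counts.** Inputs: 60 patients per arm (Protocol 7.7), all assumed treated. The event counts are assumptions, because the documents give no on-trial rate of death or fatal ICH. The intervals are exact (Clopper-Pearson) 95% limits.

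- One event, in a patient of the third row, included: 1/60 = 1.67%. The lower limit is 1 − 0.975^(1/60) = 0.04%. The upper limit solves (1−p)^60 + 60p(1−p)^59 = 0.025, giving 8.94%.
- The same patient excluded and removed from the denominator: 0/59 = 0%. The upper limit is 1 − 0.025^(1/59) = 6.06%.
- Two events, one in such a patient: 2/60 = 3.3% (0.4–11.5%) against 1/59 = 1.7% (0.04–9.1%).
- With the 54 evaluable patients per arm of Protocol 7.7: 1/54 = 1.9% (0.05–9.9%) against 0/53 = 0% (0–6.7%).

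The intervals overlap in every case. What changes is whether the event appears at all.

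**The case against.** The best defence is that the second limb speaks of other reasons, which implies that death is itself meant as one reason for having no usable scan. Read with the fallback just before it, the section would then be coherent: no usable scan from any cause means exclusion, and a death with a usable scan is classified. The authors may well have meant this. It stands as a possible reading, but the text does not secure it. The first limb turns on the absence of an EOT scan, not of any scan, and the on-treatment alternative was added only to the second.

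A second objection also stands. The fallback names only the judgement of worsening, so its reach to new ICH is less explicit. This limits how far the fallback alone contradicts the exclusion. It is also a second gap that the same edit should close.

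A reader might infer more than the documents support:

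- *That leaving out patients without a usable scan is itself a departure from the protocol.* It is not. Protocol 7.3.2 leaves detail to the SAP, and SAP 6.3 warns: "Note that the number of patients with available data for an endpoint may differ".
- *That the rule breaches Protocol 3.3.4.1, which says "Data collected for all randomised patients will be used in the analysis".* That is a general statement in a section on stopping study drug, and it extends to randomised patients who never took any. This endpoint is analysed on the treated set, so the statement cannot govern it literally.
- *That fatal ICH disappears from the report.* Symptomatic intracranial bleeding and fatal bleeding are major bleeds under SAP 5.1 and count in the primary composite. Protocol 5.3.5.2 sub-classifies fatal major bleeds, and SAP 7.8.1 tabulates adverse events leading to death.

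**Conclusion.** The point holds as a wording defect. Followed as written, SAP 5.2.2 makes an outcome-dependent exclusion from a safety endpoint, at odds with its own fallback and with the imaging sources in Protocol 5.3.5.1. The documents do not show that this was a deliberate choice.

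The affected group is narrow: patients with an analysable on-treatment scan, up to 6 days after last intake, who then died before an EOT scan. Only this exploratory secondary endpoint and its separately presented components are touched, and no hypothesis is tested on them. The documents give no basis for estimating how many patients would be affected. The 1.7% against 0% contrast is an illustration that assumes one such event in an arm of 60, no other ICH event in that arm, and removal of the patient from the denominator. It shows a lost event, not a changed inference.

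**What to change.** In SAP 5.2.2:

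1. Delete the stand-alone death clause, so that a patient, deceased or not, is excluded only when neither an analysable EOT scan nor an analysable on-treatment scan exists.
2. State that the on-treatment fallback applies to both components, new ICH and worsening, including for patients who died.

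Optionally, report the number excluded by arm.

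The cost is a small edit to the SAP text and the matching derivation. No new data or protocol amendment is needed, because the worsening-triggered and EOT images already go to the Adjudication Committee. If the milder reading was intended all along, the edit simply makes it explicit.
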